STUDY PROTOCOL AND STATISTICAL ANALYSIS PLAN

NCT Number: *Not Yet Assigned*

Official Title: *The Role of Musical Stimulation Intensity on Postural Control in Athletes: A Virtual Reality-Based Posturography Study*

Document Type: Study Protocol and Statistical Analysis Plan

Ethics Approval: Malatya Turgut Özal University Health Sciences Scientific Research Ethics Committee

Approval Number: 2025/95

Date: 28 October 2025

Sponsor-Investigator: Asst. [name]. [name]

Affiliation: Malatya Turgut Özal University, Malatya, Türkiye

1. Background and Rationale

Postural stability depends on the integration of visual, vestibular, and somatosensory inputs for equilibrium control. Auditory stimulation, particularly music, can modulate standing posture through mechanisms such as attentional modulation and stochastic resonance, which may alter proprioceptive feedback and motor strategies. The influence of different music intensity levels on balance performance in athletes remains insufficiently studied, especially using virtual reality-based posturography. This protocol evaluates how auditory intensity modulates sensory reweighting and stability indices in sport-trained individuals.

2. Objectives

Primary Objective

To investigate the effects of different musical intensity levels (low, medium, high) on postural control in athletes using VR-based posturography.

Secondary Objective

To explore whether individual noise sensitivity moderates balance performance during auditory stimulation.

3. Study Design

This experimental, cross-sectional study used a randomized crossover design. Each participant completed balance assessments under three musical intensity conditions (low ≈ 55 dB, medium ≈ 70 dB, high ≈ 85 dB). Conditions were presented in randomized order, and a ≥ 60 -second washout period was provided between trials to minimize carryover effects.

4. Participants

Inclusion Criteria

- Age 18–30 years
- Active athletic training ≥ 5 years
- Normal hearing thresholds (≤ 20 dB HL)
- No vestibular, neurological, orthopedic, or psychiatric disorders
- Written informed consent

Exclusion Criteria

- Current or past vestibular disorder or vertigo
- Intolerance to auditory stimulation
- Ototoxic drug use in the last 3 months
- Abnormal tympanometry

5. Intervention Description

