Auditory stimulation consisted of *Mozart's Jupiter Symphony*, delivered via standardized VR-integrated headphones (Balance VR system). All participants listened to the same musical excerpt at three intensity levels. Balance evaluations were conducted using VR-based CTSIB and Limits of Stability modules.

6. Outcome Measures

Primary Outcomes

- CTSIB composite equilibrium score
- Sensory component scores: somatosensory, visual, vestibular, and visual preference

Secondary Outcomes

- LOS metrics: reaction time, endpoint excursion, maximum excursion, mean velocity, and directional control
- Noise sensitivity measured using the Weinstein Noise Sensitivity Scale (Turkish validated version)

7. Statistical Analysis Plan

Normality was assessed using the Shapiro–Wilk test. The effects of auditory intensity and sport type were analyzed using repeated-measures ANOVA and linear mixed models. Bonferroni correction was applied for post-hoc pairwise comparisons. Pearson correlations were performed to examine the association between noise sensitivity and postural outcomes. Partial eta-squared (η^2) was used to estimate effect size. Significance level: **p < 0.05** (two-tailed).

8. Ethics and Data Handling

The study was approved by the Malatya Turgut Özal University Health Sciences Scientific Research Ethics Committee (Approval No: 2025/95) and adhered to the Declaration of Helsinki. All participants signed written informed consent. Data are anonymized and securely stored. Individual participant data will **not** be publicly shared due to institutional data protection regulations; only aggregated results may be reported.

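### Bonferroni for the three intensity pairs is valid but stricter than needed: on the same p-values, a step-down rule keeps 5% familywise error per outcome and can only add findings

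*Combined protocol and SAP*

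**What the plan says.** Section 3 (Study Design) gives three intensity levels within person: "This experimental, cross-sectional study used a randomized crossover design" and "Each participant completed balance assessments under three musical intensity conditions". That makes three paired contrasts: low-medium, medium-high and low-high.

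Section 7 (Statistical Analysis Plan) names the models, "The effects of auditory intensity and sport type were analyzed using repeated-measures ANOVA and linear mixed models", and then the multiplicity rule, "Bonferroni correction was applied for post-hoc pairwise comparisons", at a two-sided 5% level.

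Section 6 (Outcome Measures) lists five primary scores: the CTSIB composite and four components, "Sensory component scores: somatosensory, visual, vestibular, and visual preference".

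The document does not say:
- what family the Bonferroni rule covers;
- whether pairs are tested only after a significant overall test;
- which error term the pairwise tests use;
- how many sport types there are;
- whether anything is adjusted across the five scores.

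It gives no sample size or power figure and promises no simultaneous confidence intervals.

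**The concern.** Single-step Bonferroni holds every pair at 0.0167, even after one pair has been declared different. With exactly three levels that is more than error control requires, because once one difference is real at most one equality can remain.

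What is at stake is limited. The overall test already addresses, at full alpha, whether intensity matters at all. The pairwise tests say which levels differ, and the primary objective is framed in terms of low, medium and high. The unnecessary strictness falls on the second and third pairs. Under a graded effect these are mainly the adjacent levels; low versus high is usually the first pair found and gains almost nothing.

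**Working it through.** **Inputs.** From the document: three conditions, paired data, two-sided alpha 0.05, Bonferroni, five primary scores. The plan has no figure of its own to reproduce. Assumed for illustration: outcome SD 1, equal correlation rho between conditions (0, 0.5, 0.8, 0.9), N 20 to 60, largest mean difference D of 0.4, 0.7 or 1.0. The SD of a paired difference is √(2(1−rho)), which is 1.41, 1.00, 0.63 and 0.45 for the four values of rho.

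**Thresholds, ordered p-values, smallest first.**
- Bonferroni: 0.0167, 0.0167, 0.0167.
- Holm: 0.0167, 0.025, 0.05.
- Step-down for three means: 0.0167, 0.05, 0.05.

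**Error control within one outcome.** There are three cases.
1. All three means equal: an error requires the smallest p-value to fall below 0.05/3. The probability is at most 3 × 0.05/3 = 0.05, whatever the covariance.
2. Exactly one pair equal: only that pair can be falsely rejected, and its threshold never exceeds 0.05.
3. No pair equal: no error is possible.

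This needs valid pairwise p-values and nothing else. Each step-down threshold is at least 0.0167 and the first is identical, so no Bonferroni rejection is lost and the chance of at least one rejection is the same.

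**Simulated error** (40,000 runs per setting, seven covariance structures including three non-spherical, N 20, 30 and 60, paired t-tests). All means equal: 3.6% to 4.8%, the same for both rules. One equal pair: Bonferroni 1.5% to 1.8%, step-down 2.1% to 5.2%. The 5.2% is within simulation error of 5%: √(0.05 × 0.95/40,000) = 0.11 point.

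**Simulated power** (96 settings, 20,000 runs each, both rules applied to the same paired t-tests). Bonferroni rejections lost: 0. Runs in which any-pair detection differed: 0 of 1.92 million.

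| Means (low/medium/high) | N | Pair | rho | Bonferroni | Step-down |
|---|---|---|---|---|---|
| 0/0/0.7 | 30 | each differing pair | 0 | 57.6% | 66.2% |
| 0/0/0.7 | 30 | each differing pair | 0.5 | 89.5% | 94.3% |
| 0/0/0.7 | 30 | each differing pair | 0.8 | 100% | 100% |
| 0/0.35/0.7 | 60 | adjacent | 0 | 30.1% | 46.5% |
| 0/0.35/0.7 | 60 | adjacent | 0.5 | 60% | 76% |
| 0/0.35/0.7 | 60 | adjacent | 0.8 | 96.2% | 98.7% |
| 0/0.35/0.7 | 60 | low-high | 0 | 91.0% | 91.9% |
| 0/0.35/0.7 | 20 | low-medium (largest gain) | 0.8 | 45.0% | 64.4% |

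Over the grid, the gain per truly differing pair is 0 to about 19 points (Holm 0 to 14). Low-high under a graded effect gains at most 2.7. In a separate run (100,000 trials; means 0/0.3/0.6, N = 30, rho 0.5), at least two pairs were found in 36.9% with Bonferroni, 45.2% with Holm and 60.2% with the step-down rule; at least one in 79.2% with all three.

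**Effect of also changing the error term.** Suppose the plan's pairs use a pooled error with 2(N−1) degrees of freedom, and the step-down rule is run on pair-specific tests with N−1. For means 0/0.35/0.7, rho 0.5, 40,000 runs:
- N = 20 (38 versus 19 df): a Bonferroni rejection is lost in 5.3% of runs, and any-pair detection falls from 75.0% to about 72.3%.
- N = 30 (58 versus 29 df): a rejection is lost in 2.2%, and detection falls from 91.9% to 90.6%.

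Losses reached about 6% in the settings tried. They shrank at larger N and came close to none where power was near 100%. With the step-down rule applied to the pooled p-values themselves, the loss is zero.

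**Across the five primary scores, independence assumed.** One pair truly equal in every score: 1 − (1 − 0.0167)^5 = 8.1% for Bonferroni; at most 1 − 0.95^5 = 22.6% for step-down. All means equal in every score: 1 − (1 − 0.0364)^5 = 16.9% to 1 − (1 − 0.0475)^5 = 21.6%, the same for both rules.

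**The case against.** The strongest reply is that nothing is broken. Bonferroni controls what it claims to control, the plan names no adjacent-level hypothesis, and choosing a step-down rule is a preference between valid methods. That stands, and it keeps this point at the lowest priority. A reader might infer that the planned analysis is invalid or that the trial is underpowered; the document supports neither.

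A reader might also infer that no rejection can be lost however the step-down rule is implemented. That is too strong. Section 7 does not say which error term the pairs use, and a simultaneous move to pair-specific standard errors can lose rejections, as shown above. Those standard errors guard against non-sphericity, which may be a good reason to use them, but that is a different decision. Likewise, adding an overall-test gate where none was planned can lose some rejections (1.2% of trials at N = 30 with steps of 0.3 SD); keeping whatever gate is already intended does not.

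Two further objections limit the benefit. The unused margin in Bonferroni gives some incidental protection across the five primary scores, and step-down gives that up. However, the plan claims no control across scores, and that question needs settling under either rule. Second, the plan is written in the past tense. A reader might infer that outcomes have already been seen; the wording does not prove it, but nothing shows that the analysis is still open either.

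**Conclusion.** The point holds as an optional improvement. For the three intensity pairs within one outcome, and on identical and valid p-values, the step-down rule keeps familywise error at or below 5%, keeps every Bonferroni rejection, leaves any-pair detection unchanged and can add second or third pairs. Those statements are general. The gain of 0 to about 19 points is illustrative and cannot be placed within that range for this trial.

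The conclusion rests on reading the family as three pairs per outcome. It does not extend to sport-type comparisons: with four or more levels several equal pairs can remain after one rejection, and the shortcut fails. It does not extend to intensity-by-sport comparisons, to a change of error term, or to error across the five primary scores. If outcomes have been seen, there is no confirmatory gain.

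**What to change.** If outcomes are unseen, replace the Bonferroni sentence in section 7 with two rules:
- *Intensity pairs.* Within each outcome, using the pairwise p-values from the planned model, test the smallest of the three at alpha/3; if it is significant, test each of the other two at alpha. Equivalently, report adjusted p-values: 3 × p_min (capped at 1) for the smallest, and the larger of 3 × p_min and p for each of the others. Holm is the simpler fallback.
- *Sport-type and intensity-by-sport comparisons.* Keep Bonferroni and state the number of comparisons.

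In the same edit, state the family, the error term used for the pairs (as a separate choice, with its reason), whether an overall test gates them, and what adjustment, if any, applies across the five primary scores. If alpha were split to 0.01 per score, the gain on the same grid would be 0 to about 16 points.

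If outcomes have been seen, Bonferroni stays primary and any step-down result is labelled post hoc.

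The cost is one sentence becoming two rules, with no new data. The downsides are the loss of simple matching simultaneous confidence intervals, which the plan does not promise, and the higher error across the five scores shown above unless that is handled.

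### The secondary objective asks whether noise sensitivity moderates balance, but the analysis plan specifies only correlations and no test of moderation

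*Combined protocol and SAP*

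**What the plan says.** The secondary objective in Section 2 reads: "To explore whether individual noise sensitivity moderates balance performance during auditory stimulation". Section 3 describes a crossover in which "Each participant completed balance assessments under three musical intensity conditions" (low, medium, high). No silent condition is described, so the factor that varies within a person is intensity.

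Section 7 mentions noise sensitivity once: "Pearson correlations were performed to examine the association between noise sensitivity and postural outcomes". The modelling sentence is separate: "The effects of auditory intensity and sport type were analyzed using repeated-measures ANOVA and linear mixed models". It does not name noise sensitivity and states no interaction.

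Section 6 lists ten postural measures: the "CTSIB composite equilibrium score" (one), the "Sensory component scores: somatosensory, visual, vestibular, and visual preference" (four) and the "LOS metrics: reaction time, endpoint excursion, maximum excursion, mean velocity, and directional control" (five). Noise sensitivity itself is listed there as a secondary outcome, not as a moderator or covariate.

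**The concern.** Moderation and association are different hypotheses. Since every condition has music and only its intensity changes, moderation here means that the effect of intensity depends on how noise-sensitive the athlete is. A correlation between noise sensitivity and the level of an outcome asks instead whether noise-sensitive athletes balance better or worse overall.

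If level correlations are used to answer the objective, two errors are possible. A significant correlation may be reported as moderation when the difference is the same at all three intensities. A null correlation with the averaged outcome may be reported as no moderation when the slopes differ between intensities.

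Section 7 also leaves open which of the ten measures are correlated, at which intensity, and whether as level, average or change. These choices can give different answers from the same data.

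**Working it through.** **Text check.** A test of moderation would have to appear in Section 7 as one of three things: a noise-sensitivity-by-intensity term, a correlation with a between-intensity change, or a formal comparison of correlations across intensities. None is there. The plan gives no figure on this point to reproduce. The number of candidate level correlations is 1 + 4 + 5 = 10 on averages, or 10 × 3 = 30 if run at each intensity.

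**Illustration with assumed inputs.** The documents give no sample size, SD or slope, so the following are assumptions. For athlete i at intensity j:

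Y_ij = s_j·x_i + b_i + e_ij

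Here x is standardised noise sensitivity, the between-person SD is 1, the within-person SD is 0.7 (variance 0.49), and errors are independent with equal variance. Two scenarios share a mean slope of −0.2: slopes −0.2/−0.2/−0.2 (no moderation) and 0/−0.2/−0.4 (moderation).

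Population correlations with x:

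- Averaged outcome: s̄ / √(s̄² + 1 + 0.49/3) = −0.2 / √(0.04 + 1.163) = −0.18 in **both** scenarios.
- Single intensity: s_j / √(s_j² + 1 + 0.49). Without moderation this is −0.2/√1.53 = −0.16 at each intensity. With moderation it is 0, −0.16 and −0.4/√1.65 = −0.31.
- High-minus-low change: (s_H − s_L) / √((s_H − s_L)² + 2 × 0.49). Without moderation this is 0. With moderation it is −0.4/√1.14 = −0.37.

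The averaged correlation depends on the mean slope, not on differences between slopes, whatever values are assumed.

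**Simulation.** 20,000 trials per setting, two-sided 0.05. The interaction test is F on 2 and 2(N − 2) degrees of freedom, from within-person contrasts. Entries are the percentage of trials significant at N = 30 / N = 50.

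| Slopes (low/medium/high) | Averaged Pearson | At least one per-intensity Pearson | Change-score Pearson | Interaction |
|---|---|---|---|---|
| −0.2/−0.2/−0.2 (no moderation) | 16 / 25 | 25 / 36 | 5 / 5 | 5 / 5 |
| 0/−0.2/−0.4 (moderation) | 16 / 24 | 45 / 64 | 55 / 78 | 46 / 70 |

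Two further cases show the extremes:

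- Slopes of −0.5 throughout (no moderation): averaged Pearson 66 / 88, interaction 5 / 5.
- Slopes of +0.4/0/−0.4 (deliberately extreme): averaged Pearson 5 / 5, at least one per-intensity Pearson about 72 / 93, interaction 95 / 99.8.

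**Sensitivity.** Over within-person SD 0.5 to 1.0 and N = 30 to 50, in the matched pair of scenarios, the averaged Pearson is significant in 15–26% of trials without moderation and 15–25% with it. The interaction test is significant in 5% without and 25–93% with.

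**The case against.** The strongest counter-argument is that the objective speaks of moderating balance performance, not of moderating the effect of intensity. With music in every condition, this could loosely mean that balance under music is related to noise sensitivity, and a correlation would then answer it. This stands as a possible reading. It moves the fault from the analysis to the objective's wording, and Sections 2 and 7 still do not match.

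Second, the text does not exclude a valid analysis. A correlation with the high-minus-low change would test moderation and could be called a correlation with a postural outcome. That is correct: the objective has no specified test, which is not the same as being untestable.

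Third, the measures themselves are listed in Section 6. So what is undefined is which of them, at which intensity and in what form.

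Fourth, per-intensity correlations do respond to moderation, as the table shows. But at least one is also significant in 25–36% of trials without it, so they do not identify moderation unless they are formally compared, and no comparison is planned.

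Finally, the objective is secondary and exploratory. This limits the weight of the point without removing it.

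**Conclusion.** The concern holds. The plan names moderation as its secondary objective and specifies no analysis that tests it. That follows from the text alone and rests on no assumed number.

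The percentages are illustrative, not estimates for this trial. They depend on the assumed slopes and SDs and on equal, independent within-person errors. The conclusion that a correlation with the averaged outcome cannot tell association from moderation does not depend on those values.

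This should be fixed, but its reach is limited to the secondary, exploratory objective. The primary objective is not affected.

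**What to change.** Specify one test of the secondary objective on a named outcome. The CTSIB composite is an obvious candidate, although Section 6 does not rank it above the four sensory scores.

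- **Option 1.** In the planned linear mixed model, add the centred noise-sensitivity score and its interaction with intensity (2 degrees of freedom if intensity is a three-level factor). Report the noise-sensitivity slope at each intensity with its 95% CI.
- **Option 2.** Name a correlation of noise sensitivity with the high-minus-low change. It is somewhat more powerful if slopes change steadily with intensity (55% against 46% at N = 30 above), but it ignores the medium condition.
- **Option 3.** If only association was meant, reword the objective to say so.

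Under Options 1 and 2, keep correlations with outcome level as descriptive, state which value of each outcome they use, and do not read them as evidence on moderation. Describe noise sensitivity as a moderator rather than an outcome.

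The cost is one sentence and two model terms, or one named correlation, or one reworded objective, with no new data. Section 7 is written in the past tense, so the change should be dated, and the test labelled post hoc if results have been seen. Power may be modest: 25–75% for the interaction at N = 30 in the assumed 0/−0.2/−0.4 case, over within-person SD 0.5 to 1.0. A null result would therefore not show that moderation is absent.

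### Section 7 correlates noise sensitivity with outcomes measured three times per athlete, but defines neither the unit of analysis nor a multiplicity rule for those correlations

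*Combined protocol and SAP*

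**What the plan says.** Section 3 describes the design: "This experimental, cross-sectional study used a randomized crossover design". It continues: "Each participant completed balance assessments under three musical intensity conditions". Section 5 states that balance was evaluated with the CTSIB and Limits of Stability modules, so each postural outcome in Section 6 has three scores from the same athlete.

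Noise sensitivity is listed in Section 6 as a secondary outcome measured by questionnaire. No repeat at each intensity is described.

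The secondary objective in Section 2 is "To explore whether individual noise sensitivity moderates balance performance during auditory stimulation". The only method that Section 7 names for it is "Pearson correlations were performed to examine the association between noise sensitivity and postural outcomes". Repeated-measures methods are named for other factors: "The effects of auditory intensity and sport type were analyzed using repeated-measures ANOVA and linear mixed models". The only multiplicity rule is "Bonferroni correction was applied for post-hoc pairwise comparisons". The significance level is 0.05, two-sided.

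**The concern.** Pearson's test assumes one independent pair per person. Here one value per athlete meets three correlated values per athlete, and Section 7 does not say whether these are stacked, split by level, averaged or differenced. The choices have very different properties. Stacking counts each athlete three times and makes the standard error too small. Splitting gives three overlapping tests per outcome. No choice comes with a correction across outcomes.

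At stake is the only analysis named for the secondary objective. Section 8 says that individual data will not be shared publicly, so an outside reader who suspected stacking could not redo the analysis with one row per athlete. The comparison of intensities under the primary objective is not affected.

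**Working it through.** The documents give no sample size, ICC or error rate for this analysis, so there is no figure of theirs to reproduce. Everything below that depends on N or ICC is an assumption, shown over a range.

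**Inputs from the documents.** Three scores per athlete per outcome (Section 3); two-sided alpha 0.05 (Section 7); postural outcomes in Section 6: 1 composite + 4 sensory components + 5 LOS metrics = 10.

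**Assumed.** One noise-sensitivity value per athlete; ICC 0.3–0.9; N = 20, 30 or 60.

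**1. Levels stacked.** With three scores per athlete against an athlete-level covariate, the variance is understated by the factor 1 + 2·ICC. The true two-sided error is 2·(1 − Φ(1.96/√(1 + 2·ICC))). For ICC 0.5 this is 2·(1 − Φ(1.96/√2.0)) = 16.6%. The simulations assume no association, with 20,000 runs per cell. In the last column, adjacent level means differ by 0.5 SD and level is ignored.

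| ICC | 1 + 2·ICC | Formula | Simulated, N = 20 / 30 / 60 | Simulated with level shift, N = 20–60 |
|---|---|---|---|---|
| 0.3 | 1.6 | 12.1% | 12.2 / 12.5 / 12.3% | 9.5–9.6% |
| 0.5 | 2.0 | 16.6% | 16.9 / 16.9 / 16.7% | 13.6–14.0% |
| 0.7 | 2.4 | 20.6% | 21.5 / 21.3 / 21.0% | 17.6–18.2% |
| 0.9 | 2.8 | 24.2% | 26.0 / 25.2 / 24.3% | 20.6–21.6% |

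**2. Levels split.** Each single-level test holds its level (simulated 4.7–5.2%). The chance of at least one false positive among the three tests of one outcome is 12–13% at ICC 0.5, about 11% at 0.7 and 8–9% at 0.9.

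Precision: the mean of three scores has (1 + 2·ICC)/3 of the variance of one score. If noise sensitivity relates equally to all levels, a single-level correlation is therefore √((1 + 2·ICC)/3) of the correlation with the mean: 0.82, 0.89 and 0.97 at ICC 0.5, 0.7 and 0.9. For example, take an assumed r = 0.40 with the mean and N = 30. Power is Φ(atanh(r)·√27 − 1.96), which is 60% with the mean and 42%, 49% and 56% with a single level.

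**3. One value per athlete.** The simulated error is 4.7–5.3% for the mean over levels and 4.5–5.3% for the high-minus-low difference. Both are valid.

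**4. Outcomes.** Even with one value per athlete, ten tests at 0.05 give 1 − 0.95^10 = 40% if independent, and less if the outcomes are positively correlated. Ten outcomes at three levels make up to 30 tests.

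**5. What the mean can miss.** Suppose the true correlation is 0.40 at the high level and zero at the other two, with ICC 0.7. The correlation with the mean is then (0.40/3)/√0.8 = 0.15.

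**The case against.** The strongest reply is that the plan omits a detail and commits no error. Nothing says that rows were stacked. The sentence on Pearson correlations fits a correlation with the athlete's mean or with a between-level difference equally well, and both hold 5%. Section 7 names repeated-measures methods in the same paragraph, so the plan recognises the repeated structure. The objective is secondary and worded as exploratory.

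Much of this stands, and it rules out three stronger readings that a reader might infer.

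- *The reported correlations carry a false-positive rate of 17–26%.* That needs stacking, which is not documented, and an ICC of about 0.5 or more, which the documents do not give. At ICC 0.3 the rate is about 12%.
- *The association has no valid form.* Splitting holds 5% per test, and so do averaging and differencing. The two costs of splitting also pull apart: near-duplicate tests need a high ICC, where the loss of precision is small.
- *The three levels produce a very large family-wise error.* For 30 by-level tests, simulation with N = 30 and correlations between outcomes of 0–0.5 gives at least one false positive in roughly 46–75% of trials. Most of that comes from having ten outcomes, and the plan does not say that all ten were correlated.

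It is also fair to object that averaging should not be imposed as the only test. The objective concerns effects that may depend on intensity, and step 5 shows how the mean can dilute them.

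What does not fall away is that the text permits an invalid analysis, states no correction for any permitted one, and leaves noise sensitivity out of the model that could handle it properly.

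**Conclusion.** The point holds as a gap in specification with real consequences, and it should be corrected. Section 7 applies plain Pearson correlation at 0.05 to outcomes with three scores per athlete, without a unit of analysis or a multiplicity rule.

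If stacked, the error is about 12–24% for an assumed ICC of 0.3–0.9, up to about 26% at N = 20, and lower if level means differ. If split, the error per test is correct, and the cost is three tests per outcome and a correlation that is 0.82–0.97 of that with the mean at ICC 0.5–0.9. On every reading up to ten outcomes are tested uncorrected.

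These figures rest on assumed N and ICC and on noise sensitivity being measured once. The documents do not support a claim that the reported results are wrong.

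**What to change.** Replace the sentence on correlations in Section 7 with wording such as:

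> Noise sensitivity is analysed in the linear mixed model already planned, with a random participant effect and terms for noise sensitivity and noise sensitivity by intensity. The interaction for the CTSIB composite is the single tested noise-sensitivity result. Pearson correlations are descriptive, use one value per athlete (the mean over the three levels, or the high-minus-low difference), and are reported with 95% CIs without a significance claim. Rows from different levels are never stacked.

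This settles the unit of analysis, limits the testing to one result, and tests the moderation question in Section 2, which a correlation with level scores or their mean does not. With intensity as a three-level factor, the interaction test has 3 − 1 = 2 degrees of freedom; the SAP should say so.

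The cost is a change of wording and one model fit, with no new data. The downside is fewer correlations to report as significant. Section 7 is written in the past tense. If the data have already been analysed, the report must disclose that the single test was chosen afterwards, and state how the three scores were handled in any correlation already computed.

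### The noise-sensitivity correlations name no adjustment for sport type, which the SAP itself analyses as a factor for balance; if noise sensitivity also differs by sport, they are confounded.

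*Combined protocol and SAP*

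**What the plan says.** The secondary objective in Section 2 is "To explore whether individual noise sensitivity moderates balance performance during auditory stimulation". Section 3 describes a randomised crossover: "Each participant completed balance assessments under three musical intensity conditions". Section 6 lists the Weinstein scale as the noise-sensitivity measure and describes no repeat of it by condition, so it is read here as one score per athlete.

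Section 7 contains two relevant sentences. On the main factors: "The effects of auditory intensity and sport type were analyzed using repeated-measures ANOVA and linear mixed models". On noise sensitivity: "Pearson correlations were performed to examine the association between noise sensitivity and postural outcomes". The second names no covariate, no stratification and no partial correlation, and noise sensitivity is not listed as a term in the mixed model.

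Sport type appears only in that sentence of Section 7. The documents do not list the sports, give the number of groups or state a hypothesis about them. Eligibility in Section 4 requires "Active athletic training ≥ 5 years" and does not restrict or stratify by sport. No sample size is given.

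**The concern.** The crossover protects comparisons between intensities, because each athlete is his or her own control and the order is randomised. It gives no protection to a comparison of athletes with high and low noise sensitivity, who may differ in other ways. Sport type is the one between-athlete factor that the SAP itself considers relevant to balance, and the noise-sensitivity analysis leaves it out.

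If athletes in some sports are both more sensitive to noise and better or worse at balance, a correlation over all athletes picks up that sport difference. The answer to the secondary objective could then reflect which sports were recruited. The same can happen in a moderation analysis: if sports respond differently to intensity and also differ in noise sensitivity, a sport effect can pass as moderation by noise sensitivity.

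**Working it through.** **Inputs from the documents.** Method: Pearson correlation, no adjustment named (Section 7). Sport type: a factor in the ANOVA and mixed models only (Section 7). Significance level: two-sided 0.05 (Section 7). There is no planned correlation, variance, sample size or power figure to reproduce.

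**Assumptions.** Three equal-sized sports, 30 or 60 athletes in total, no association between noise sensitivity and balance within any sport. Let s_x and s_y be the shares of variance in noise sensitivity and balance that lie between sports, and let a be the correlation between the two sets of sport means (1 = full agreement, 0.5 = half agreement).

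**Formula.** With no within-sport association, all covariance is between sports, so the pooled correlation is r = a × √(s_x × s_y). For example, s_x = s_y = 0.20 with a = 1 gives r = 0.20, and s_x = s_y = 0.10 with a = 0.5 gives r = 0.05. If s_x = 0, then r = 0 whatever s_y is.

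**Simulated rate of p < 0.05 for the unadjusted correlation** (8,000 to 20,000 runs per cell; independent runs agreed to within about 2 percentage points):

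| Sport share: noise sensitivity / balance | Agreement | Pooled r | n = 30 | n = 60 |
|---|---|---|---|---|
| 0% / 20% | – | 0 | about 5% | about 5% |
| 5% / 5% | half | 0.025 | 5.3% | 5.4% |
| 10% / 10% | half | 0.05 | 5.7% | 6.7% |
| 2% / 20% | full | 0.06 | 6.5% | 7.4% |
| 10% / 10% | full | 0.10 | 8% | 12% |
| 20% / 20% | half | 0.10 | 8% | 12% |
| 20% / 20% | full | 0.20 | 19% | 34% |
| 30% / 30% | full | 0.30 | about 38% | about 67% |

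The partial correlation given sport type rejected in about 5% of runs throughout (4.5–5.5%).

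**Second set-up.** With two equal sports whose means differ by d_x and d_y within-sport standard deviations, r = 0.25·d_x·d_y / √[(1 + 0.25·d_x²)(1 + 0.25·d_y²)]. For d_x = d_y = 1 this is 0.25/1.25 = 0.20, and the unadjusted test rejected in 34.0% of runs at n = 60. For d_x = d_y = 0.5, r = 0.0625/1.0625 = 0.06 and the rate was 7.4%. For d_x = 0 and d_y = 0.8 it stayed near 5%. After adjustment it was 4.7–5.4% throughout. The mechanism does not depend on how the sports are modelled.

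**Does adjustment alone answer the objective?** No. Suppose noise sensitivity shifts balance by the same amount at every intensity (assumed slope 0.5), so there is no moderation. The correlation at one intensity was then significant in 72% of runs at n = 30 and 95% at n = 60, while the correlation with the difference between two intensities stayed near 5%. Moderation needs a noise-sensitivity-by-intensity term.

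**The case against.** The strongest reply is that confounding needs two links, and the documents establish neither. A reader might infer that the plan expects balance to differ by sport. It does not say so: "The effects of auditory intensity and sport type were analyzed" describes testing a factor, with no hypothesis attached. A reader might also infer that a balance difference between sports is enough to bias the correlation. It is not; the first row of the table shows no inflation. Nothing in the documents links sport to noise sensitivity, and several plausible rows lie within one to three points of 5%. That the correlation is taken over all sports together is itself read from silence, although it is the natural reading.

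The objective is also exploratory and the analysis is described as an association, for which an unadjusted correlation is a legitimate descriptive summary. If noise sensitivity influences which sport a person takes up, sport lies downstream of it, and the adjusted value is not automatically the right one.

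These points stand, and they make the concern conditional. They do not justify leaving the adjustment out. Exploratory status does not remove confounding. If sport is unrelated to noise sensitivity, adjustment costs little; if it is related, only the adjusted value separates the two. The doubt about direction is a reason to show both values.

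The case is weaker for age and years of training. No calculation supports them, age is limited to 18–30, and the training criterion can be checked as yes or no, so it cannot be assumed that years of training are on file as a number.

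**Conclusion.** The point holds in conditional form. Section 7 names an unadjusted correlation for a non-randomised, between-athlete trait and leaves out sport type, which the same section analyses for balance. If noise sensitivity also differs by sport, the correlation is confounded. Under the stated assumptions the false-positive rate runs from the nominal 5% to 34% at n = 60 in the strong case of 20% shares with full agreement, and higher only beyond that.

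The documents do not support the stronger reading that the correlation is biased, because they are silent on noise sensitivity by sport and give neither the number of sports nor the sample size. The actual bias cannot be determined. This is a worthwhile improvement to a secondary analysis; it does not affect the primary comparison of intensities. Sport adjustment of a correlation with balance level would still leave the moderation objective unanswered.

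**What to change.** In Section 7:

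1. Report the association of noise sensitivity with each postural outcome adjusted for sport type, as a partial correlation or regression coefficient, with the unadjusted Pearson r beside it.
2. For the secondary objective, use the linear mixed model already planned for intensity and sport type. Add noise sensitivity, noise sensitivity by intensity, and intensity by sport type. Name the noise-sensitivity-by-intensity term as the test of moderation.
3. Treat age and years of training as optional further covariates, to be used only if recorded as values.

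The cost is SAP wording and a little code. No new data are needed, since sport type must be recorded for the analysis already planned. The downside is a few residual degrees of freedom: with three sports, the partial correlation has n − 4 in place of n − 2, so 26 in place of 28 at n = 30.
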